### 7.5 Descriptive Analysis of Outcomes Among Treated Patients

Objective 2 effectiveness analyses (described above) provide an estimate of the intervention effect among patients with an OUD diagnosis who were in an intervention versus control clinic, regardless of whether the patient was actually treated by the NCM. For example, among patients with an OUD diagnosis at baseline, some may have left the HCS, some may not be interested in receiving medication treatment for OUD, and some may be seeking treatment externally (e.g., via methadone maintenance). We therefore plan to additionally describe patient-level outcomes (e.g., acute care utilization, days of OUD medication treatment) among patients with an OUD diagnosis pre-randomization across levels of engagement with the NCM (e.g. seen by the NCM vs not).

We also plan to conduct descriptive analyses to characterize whether OUD treatment is being provided elsewhere within HCS before the patient sees the NCM, and is transferred to the PROUD intervention clinic, by describing the number of days of OUD treatment (pre- and/or post-randomization) a patient received prior to their first visit with the NCM using the most inclusive secondary measure (e.g., including dispensed buprenorphine; see Section 5.2.4).

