7.1.1 PROUD Intervention: Implementation of the MA Model

Overview and Duration. Clinics randomized to the PROUD intervention will be asked to implement collaborative care for OUDs consistent with the MA Model. The intervention is funded for 2 years. This includes 6 months start-up (hiring, training and policy development) and 18 months for induction of an estimated 1-3 patients a week (~75-225 total), as well as continued care with buprenorphine and naltrexone. The intervention consists of 3 strategies used for implementation. These 3 strategies are described immediately below. The detailed outline of each element of the MA Model that will be implemented by PROUD Intervention clinics and the Draft PROUD Manual are described below (Appendix B).

Strategy #1: Providing Funding and Guidance to Hire a NCM. First, Site PIs and health system leaders will be notified they were selected for the trial. A phone meeting will orient them towards hiring even before the in-person kickoff meeting. After kickoff, when clinics randomized to the PROUD intervention will be announced, clinic leaders and providers who have agreed to prescribe buprenorphine and naltrexone will be notified that they will receive resources and support to implement the MA Model. The clinic randomized to the PROUD intervention will be provided funding for 1.0 FTE salary for a NCM for 2 years. The clinic and health system will then recruit, hire, and onboard the NCM, supported by the project. Hiring two NCMs to share a full-time position is also an option.

The nurse care manager (NCM) is a dedicated person in the primary care clinic who works with a group of primary care doctors, nurse practitioners, and physician assistants to support management of patients on buprenorphine and injectable naltrexone for OUDs. Table 5 outlines the roles and responsibilities of the NCM (also included as part of Appendix A).

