9.3.2 Site Teams

During Period 2, the clinics randomized to the PROUD intervention will be provided funding for the NCM. The sites will hire the NCM as soon as possible within 1-6 months (ideally someone experienced in addictions treatment or mental health care). The sites ensure the following take place: credentialing; arranging local supervision for the PROUD NCM; and developing a system for a registry in or outside the EHR. The site sends the PROUD NCM to Boston to be trained by the Technical Assistance (TA) team and begins OUD treatment in the PROUD PC clinic according to the MA Model Manual. During this time the NCM works with prescribers to define local policies (e.g., regarding urine screens demonstrating drug use). PC providers who will prescribe buprenorphine obtain DEA waivers to prescribe buprenorphine if they do not have one already and identify their mentors (locally or virtually via PCSS). Sites begin sending reports to the TA Team and Lead Node Team weekly.

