### **2.4 Follow-up or “Post-randomization” Period**

Unless otherwise specified, the follow-up period is defined as the period from study day 1 to 2 years after the randomization date (or 1.5 years for one health system that randomized 6 months late). For simplicity, throughout the SAP this follow-up (“post-randomization”) period is referred to as 2 years.

[figure not shown]

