#### **4.2 Definition of Objective 2 Effectiveness Outcome Measure (Powered Secondary Outcome)**

The primary effectiveness (Objective 2) endpoint is a person-level count measure of the number of days of acute care utilization in the follow-up period, among patients with an OUD diagnosis pre-randomization. This measure includes visits to urgent care clinics or emergency departments (EDs), as well as days hospitalized. Acute care utilization will be determined from the EMR and insurance claims data when available.

For hospitalizations, the number of inpatient days will be the number of days from admission to discharge, inclusive. For urgent care or ED (referred to collectively as “emergency care”), each unique date with a visit to an urgent care or ED will be counted as 1 day (even if the patient stays overnight), except in the uncommon event that an ED visit spanned 3 or more days ( $< 0.5\%$  of ED records collected in Data Pull 4, including both randomized and non-recruited UPC clinics), in which case the encounter will be classified as a hospitalization (as patients may be boarded in an ED until a hospital bed becomes available and some are subsequently discharged from the ED if no hospital bed ever became available). If a patient is admitted from urgent care or an ED, the ED or urgent care day is not (double) counted when counting the number of days of acute care.

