#### **5.5.1 Rationale for Conducting Analyses Within a Secondary Sample**

It is expected that some of the patients who initiate treatment in PROUD intervention clinics will have been diagnosed with OUDs after randomization, potentially due to the PROUD intervention. It is also possible that patients may be newly attracted to the clinic (or to the health system entirely) potentially because of the PROUD intervention (based on the fact that at least 77% of patients treated in MA were new to the clinic after implementation). The primary analysis of Objective 2 described above would miss any impact of the PROUD intervention on both of these subsamples of patients, because they were not identified pre-randomization (because they were not previously diagnosed with OUDs or because they did not visit the clinic in the pre-randomization period). These secondary analyses within the secondary Objective 2 study sample, which includes patients seen in the trial clinics with an OUD diagnosis post-randomization only, are designed to capture these additional patients who may be affected by the PROUD intervention.

On the other hand, these secondary analyses must account for the fact that patients with newly recognized OUD in the PROUD intervention clinics post-randomization are likely to differ markedly from patients with newly recognized OUD in the UPC clinics post-randomization. Further, it is likely that these patients could differ in ways that may be associated with acute care utilization (e.g., patients could be referred for ongoing buprenorphine treatment from an ED or hospital that started treatment). To address this, analyses will adjust for covariates known or hypothesized to be associated with acute care utilization (based on prior literature), as well as secondarily for any additional covariate observed to differ across patients with newly recognized OUD post-randomization in the UPC versus PROUD intervention clinics.

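### SAP 7.5 sets no time origin for acute care by nurse-care-manager contact, so an unknown share of the engaged group's follow-up precedes that contact

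*SAP*

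**What the plan says.** SAP 7.5 explains that the Objective 2 effect estimate includes patients whom the NCM never treated. It therefore adds a description of patient-level outcomes, acute care utilization among them, "among patients with an OUD diagnosis pre-randomization across levels of engagement with the NCM (e.g. seen by the NCM vs not" (OUD is opioid use disorder). It states no window, index date or landmark, and no table shell in SAP 10.2 covers this tabulation.

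The general definitions therefore apply. SAP 4.2 makes acute care a "person-level count measure of the number of days of acute care utilization in the follow-up period". SAP 2.4 says that "the follow-up period is defined as the period from study day 1 to 2 years after the randomization date", with 1.5 years in one health care system (HCS).

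The NCM is not available on day 1. Protocol 7.1.1 allows "6 months start-up (hiring, training and policy development) and 18 months for induction of an estimated 1-3 patients a week". Protocol 9.3.2 says "The sites will hire the NCM as soon as possible within 1-6 months", and Protocol 9.3.3 puts NCM training at about 4 months.

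The date of a patient's first NCM visit is already used in the second paragraph of SAP 7.5, but only to count OUD medication days received before it.

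**The concern.** Patients are grouped by something that happens during follow-up, while the outcome is counted from the start of follow-up. Two problems follow.

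- **Misplaced time.** Acute care before the first NCM visit cannot reflect NCM contact, but it enters both the numerator and the denominator of the seen group. Any real difference after contact is diluted.
- **Unequal observability.** To be classed as seen, a patient must remain in the system until the visit. A patient not seen need not. SAP 7.5 itself notes that some patients may have left the HCS. SAP 5.4.2 says a departed patient cannot be told from one with no acute care, and SAP 8.1 reads absence of a record as absence of an event. Departed patients can therefore lower the rate in the group not seen.

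Readers are likely to use this table to interpret a null or positive intention-to-treat result, because it is the only planned description of acute care by actual NCM contact. With the clock running from randomization, it is poorly suited to that use.

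**Working it through.** **Figures in the plan.** The documents give no figure for the share of follow-up, or of acute-care days, before the first NCM visit, so there is none to reproduce. The nearest related figures are the proportions needing treatment in SAP 6.2.2. They follow from (1 − RR_ITT)/(1 − RR_treated): for RR_ITT = 0.65, 0.35/0.9 = 38.9% and 0.35/0.8 = 43.8%, against 39% and 44% stated. They reproduce. This shows that the SAP applies its RR of 0.1 or 0.2 to the whole two-year count. SAP 6.2.1 defines that RR for sustained medication treatment against no treatment, not for NCM contact. The value 0.2 below is therefore an assumption about rates after versus before a visit, not a SAP parameter.

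**Step 1: share of follow-up before the first visit.** Let s be the month the NCM starts and f = (mean month of first visit)/24. The mean is s + 1.5 if all are seen within 3 months, s + (24 − s)/3 for linearly falling intake, s + (24 − s)/2 for uniform intake, and s + 2(24 − s)/3 for linearly rising intake. The start months come from Protocol 7.1.1, 9.3.2 and 9.3.3. The intake shapes are assumptions.

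| Assumed intake | Mean first visit (month) | f |
|---|---|---|
| All within 3 months, start month 1 | 2.5 | 10.4% |
| All within 3 months, start month 4 | 5.5 | 22.9% |
| All within 3 months, start month 6 | 7.5 | 31.25% |
| Falling from month 6 | 12 | 50.0% |
| Uniform from month 1 | 12.5 | 52.1% |
| Uniform from month 4 | 14 | 58.3% |
| Uniform from month 6 | 15 | 62.5% |
| Rising from month 6 | 18 | 75.0% |

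In the HCS with 18 months of follow-up and a month-6 start, the shares are 7.5/18 = 41.7% (all within 3 months), 12/18 = 66.7% (uniform) and 14/18 = 77.8% (rising).

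**Step 2: what the table would show.** Let r be the acute-care rate after the visit relative to before it. Over the whole follow-up the engaged group shows f + (1 − f)r, relative to its own pre-visit rate. This equals the ratio to patients not seen only if they run at that same pre-visit rate. With r = 0.2:

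- f = 25%: 0.25 + 0.75 × 0.2 = 0.40
- f = 50%: 0.50 + 0.50 × 0.2 = 0.60
- f = 62.5%: 0.625 + 0.375 × 0.2 = 0.70

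**Step 3: share of acute-care days before the visit.** This is f/[f + (1 − f)r].

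| f | r = 1 | r = 0.5 | r = 0.2 |
|---|---|---|---|
| 10.4% | 10% | 19% | 37% |
| 22.9% | 23% | 37% | 60% |
| 62.5% | 62.5% | 77% | 89% |

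Pre-visit days become the majority when f exceeds r/(1 + r). That is a mean first visit after month 12 (r = 1), month 8 (r = 0.5) or month 4 (r = 0.2).

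**The case against.** The strongest reply is that SAP 7.5 is labelled descriptive, plans no model or test, and claims no effect of being seen. That stands, and it limits the importance of the point. It does not remove the need for a time origin, because a table of rates by group still needs a defined clock.

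A second reply is that SAP 5.4.5 already restricts time to the period when the NCM was seeing patients. That restriction is set by clinic. It removes start-up time but leaves each patient's own wait in place, and it belongs to the comparison of arms.

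Several stronger readings are tempting, and the documents do not support them:

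- **That most follow-up precedes the visit.** This needs a mean first visit after month 12. Slow intake makes it plausible: SAP 1.2.2 says that in early July 2019 no site was consistently reaching its weekly goal, and Protocol Modification #8 reports NCM caseloads of 0 to 34. But those facts, and the Protocol 7.1.1 schedule, concern all NCM patients. SAP 7.5 covers only patients already diagnosed before randomization, who may have been seen early.
- **That pre-visit care is pre-treatment care.** SAP 7.3 tracks transfers already on medication when they reach the NCM. Their number is not given.
- **That referral from acute care would make engaged patients look worse.** SAP 5.5.1 does say "patients could be referred for ongoing buprenorphine treatment from an ED or hospital that started treatment", but of patients with newly recognized OUD after randomization, whom SAP 7.5 excludes. No document figure supports a raised pre-visit rate in the SAP 7.5 sample.
- **That this is the plan's only view of treated patients.** SAP 5.2.6 analyses treated patients, though for medication outcomes and not acute care.

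**Conclusion.** The point holds in a limited form. SAP 7.5 classifies patients by a post-randomization event and, by default, counts their acute care from randomization. An unknown and possibly majority share of the engaged group's follow-up and acute-care days then falls before the first NCM visit. The 10% to 75% range rests on assumed intake patterns; the actual value needs first-visit dates that the documents do not contain. The dilution in step 2 also rests on an assumed rate ratio of 0.2 and on a comparison group running at the engaged group's pre-visit rate. The bias from unequal observability cannot be sized from the documents. The consequence is confined to one descriptive table, and it is worth correcting because the correction is cheap.

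**What to change.** In SAP 7.5:

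1. Report the distribution of time from randomization to first NCM visit in the Objective 2 primary sample.
2. Make a landmark comparison the lead presentation. At fixed times, for example 6 and 12 months, class patients by whether the NCM has seen them by then, and count acute-care days per person-year only afterwards. Restrict both groups to patients still active in the HCS at the landmark. SAP 5.4.2 defines activity over the whole follow-up, so this needs a version judged at the landmark.
3. For engaged patients, also report rates before and after the first NCM visit. State that acute care that triggers a referral would inflate the rate before the visit and exaggerate the fall, and that transfers were already on treatment.
4. State that engagement is self-selected and that the comparison is descriptive.

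First-visit dates can be derived from the masked NCM provider IDs that Protocol Modification #21 says sites will be asked to provide.

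The cost is minor programming and some precision. Landmarks at 6 and 12 months leave 18 and 12 months of follow-up in most systems (24 − 6 and 24 − 12), and 12 and 6 months in the late-randomized system (18 − 6 and 18 − 12). Patients first seen after a landmark count as not engaged, which dilutes the contrast; showing two landmarks makes this visible.

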#### **7.6 Descriptive Information on Data Sources**

We will describe the proportion of patients within each HCS with claims data available, which is expected to include most of the sample for one of the HCS and 10-30% enrolled patients from a second HCS. We will look at this overall and by clinic (intervention vs. control).

#### **7.7 Health Care System-specific Descriptive Analyses of Outcome Measures**

Because some HCS may have had different degrees of success in implementation, we plan to describe primary and secondary study outcome measures by study arm within each health care systems.

## 8.0 OTHER CONSIDERATIONS

### 8.1 Missing Data

Given that the primary and secondary outcomes rely on the EHR data or insurance claims data, if there is no evidence of a particular event, such as provision of buprenorphine or a visit to the ED, we will assume that the event did not occur. These same assumptions apply to the only covariate in the primary analyses of the primary Objective 1 and Objective 2 measures (baseline value of the respective measure in the 2 years prior to randomization).

Our primary Objective 1 outcome uses medication orders to capture days of OUD medication treatment as orders were available for all health systems and dispensings are considered incomplete at 5 of the 6 health systems. However, because dispensing data and not medication orders are considered the gold standard, we will conduct sensitivity analyses in which we estimate the primary outcome at each health system using only medication dispensing data in the 3 health systems that have some dispensing data and pharmacies in both the usual care and intervention clinics (Section 5.2.4).

For Objective 2, given our visit-based sample we are not able to identify when a patient is no longer observable. To address this, we will conduct a sensitivity analysis for our Objective 2 outcome among the two health systems that are health insurance plans in which we use enrolled samples (Section 5.4.3). We will also conduct sensitivity analyses that restrict to patients with evidence of being active in the health system post-randomization (as described above in Section 5.4.2).

Secondary analyses of the primary Objective 1 outcome and Objective 2 outcomes adjust for additional covariates as described above. Based on explorations of covariate distributions in prior data pulls (e.g., data pull 4), we anticipate that fewer than 6% of patients will have a missing value for any one of the individual covariates being considered (See Table 7). For Objective 1, in defining clinic-level covariates (e.g., proportion of patients with commercial insurance), we plan to exclude patients with missing covariate values when calculating clinic-level measures. For example, we will estimate the proportion of a clinic's patients who are commercially insured based on those with non-missing insurance status. Similarly, we will calculate the average neighborhood-level SES measures for a clinic based on patients with non-missing values (i.e., who have a zip code that was able to be linked to the census data). For Objective 2, for patients with missing covariate values, we plan to apply either mean imputation (for continuous covariates) or to use the indicator method (for categorical variables; i.e., by including a "missing" category).

Table 7: Missingness in Covariates among Primary Care Patients with a Visit to one of the 12 Randomized Clinics During the Pre-randomization Period (N = 291,136 patients), Based on Data Pull 4	
Covariate*	N (%) of patients with missing/unknown
Gender	4 (0.00%)
Race/ethnicity (combined version**)	16,825 (5.78%)
Insurance status (no insurance record, or recorded value listed as "unknown")	11,082 (3.81%)
Neighborhood-level SES	
No zip code available to link to census data	4,422 (1.52%)
No zip code or zip code does not link to valid value	5,906 (2.03%)

* Only covariates with any missingness are shown; diagnosis-based measures (e.g., comorbidity flags) are assumed to not be present if a diagnosis is not documented
 
** HCSs ask about race/ethnicity in different ways: in some health systems, race is not documented if the patient reports ethnicity as Hispanic; thus, the combined race/ethnicity is used for covariate adjustment
	

## **9.0 SAFETY AND INTERIM ANALYSES**

Due to the nature of this study—testing an implementation intervention, with all care provided by the health systems and using only secondary data—there are no formal interim analyses of safety performed. Further, all clinical care—and therefore responsibility for the quality of care—in this cluster-randomized pragmatic quality improvement trial is provided by the health systems. Therefore, this study monitored diverse measures of interest for the DSMB, including deaths and overdoses, but was not be able to intervene on the basis of any data and had no formal interim analyses linked to stopping rules. Since all care is provided by the health system, not the study, it would not be appropriate to intervene at the patient or provider level for any safety issue.

## 10.0 Table Shells

### 10.1 Objective 1 Paper

Table 1a. Characteristics of clinics' patient population in the pre-randomization period.		
	6 intervention clinics (No. patients =)a	6 usual care clinics (No. patients = )a
	Clinic Mean (SD)	
Staffing and Size of Clinics		
Number of providers (MD, PA, ARNP) in clinic b		
Number of buprenorphine prescribers in clinic c		
Number of patients seen in clinic		
Proportion of Clinics' Patient Population		
Age, years		
16-17		
18-24		
25-44		
45-64		
65-74		
75+		
Female		
Race/ethnicity		
Hispanic ethnicity		
Non-Hispanic		
Asian		
Black or African American		
American Indian / Alaska Native		
Native Hawaiian or Pacific Islander		
White		
Multiple race		
Other race		
Missing race and ethnicity data		
Insurance status closest to randomization		
Medicare		
Medicaid		
Otherwise insured (e.g., commercial, private)		
Uninsured		
Unknown		
Patients' neighborhood e		
Median household income		
% unemployed		
% below federal poverty level		
Rurality-urbanicity f		
Urban		
Suburban		
Rural		

Table 1a. Characteristics of clinics' patient population in the pre-randomization period.		
	6 intervention clinics (No. patients =)a	6 usual care clinics (No. patients = )a
	Clinic Mean (SD)	
Housing instability g		
Any mental health diagnoses g		
Depression		
Anxiety		
ADHD		
PTSD		
Schizophrenia/psychoses		
Other mental health conditions		
Any non-opioid SUD diagnoses g		
Tobacco		
Alcohol		
Cannabis		
Stimulant		
Other		
Other diagnoses g		
HCV infection		
HIV infection		
Non-cancer pain		
Elixhauser Comorbidity Index h		
0		
1		
2+		
a All patients with an eligible PC visit to one of the PROUD trial clinics during baseline (prior to randomization) b Number and type of providers determined from encounter data in the electronic health record c Prescribers determined from medication orders in the electronic health records. Providers assigned to clinics based on number of visits with patients in the clinic pre-randomization. d At eligible visit closest to and prior to randomization e Using zip code closest to randomization date f based on rural urban commuting codes (RUCA) g based on International Classification of Disease codes 2 years prior to randomization h It is standard to calculate the Elixhauser using 1 year of data and thus was calculated using data in the year prior to randomization Abbreviations: ADHD – attention deficit hyperactivity disorder; OUD – opioid use disorder; PTSD – post-traumatic stress disorder; SD – standard deviation; SUD – substance use disorder		

Table 1b. Opioid use disorder (OUD) and OUD treatment related characteristics of clinics in the PROUD trial in the 2 years prior to randomization, N=12		
	6 intervention clinics (No. patients =)a	6 usual care clinics (No. patients = )a
	Mean (SD) across clinics per 10,000 patients seen in the clinic pre-randomization	
Patient years of OUD treatment with buprenorphine or XR-NTX, pre-randomization a		
Proportion of clinics' patient population pre-randomization with:		
OUD diagnosis		
Opioid overdose		
Other drug overdoses		
OUD treatment a		
Buprenorphine for OUD		
XR-NTX for OUD		
80% of days covered by OUD treatment		
≥ 6-months retention in OUD treatment b		
Discontinuation of OUD treatment c		
Buprenorphine daily dose ≥16 mg		
Naloxone prescribed		
a Defined as having a medication order or procedure code for buprenorphine formulations that are indicated for OUD or having a medication order or procedure code for XR-NTX and 2+ visits with diagnosis code for OUD or opioid overdose during the pre-randomization period. b Restricted to subjects who entered the sample (i.e., had a PC visit) in the 6 months-2.0 years prior to randomization to allow for at least 6 months of follow-up c Defined as a gap in OUD treatment of 60 days d at any time during pre-randomization treatment Abbreviations: OUD – opioid use disorder; SD – standard deviation; XR-NTX – extended release injectable naltrexone		

**Table 2.** Clinic level primary and secondary implementation outcomes of the Primary Care Opioid Use Disorders Treatment (PROUD) trial, during 2 years post randomization.

Implementation measures	6 intervention clinics	6 usual care clinics	P value a
	Mean (SD) across clinics per 10,000 patients seen in clinic post randomization		
Patient years of OUD treatment (primary outcome b )			
Proportion of clinics' patient population post-randomization with:			
Any OUD diagnosis post-randomization			
Any OUD treatment b			
80% of days covered by OUD treatment			
≥ 6-months retention in OUD treatment b,c			
Discontinuation of OUD treatment b,d			
Buprenorphine daily dose ≥16 mg e			
Naloxone prescribed			
Number of buprenorphine prescribers f			

a Random effects model adjusted for the outcome measure at baseline (two years prior to randomization)

b Treatment defined as having a medication order or procedure code for buprenorphine formulations that are indicated for OUD or having a medication order or procedure code for XR-NTX and 2+ visits with diagnosis code for OUD or opioid overdose (diagnosis codes can be during the 2-years pre or 2-years post randomization).

c Restricted to subjects who entered the sample (i.e., had a PC visit) in the 1 day to 1.5 years post randomization (1 day to 12 months for the site randomizing 6-months late) to enable at least 6 months of follow-up

d Discontinuation defined as a gap in OUD treatment of 60 days

e At any time during OUD treatment post randomization

f Prescribers determined from medication orders in the electronic health records. Providers assigned to clinics based on number of visits with patients in the clinic post-randomization.

Abbreviations: NCM – nurse care manager; ITT- intent to treat; OUD: opioid use disorder; SD – standard deviation; XR-NTX – extended release injectable naltrexone

Supplemental Table 1a is the main Table 1a above by health system
Supplemental Table 1b is the main Table 1b above by health system
Supplemental Table 2 is the main Table 1a above but using data for the post randomization period and among patients with an eligible visit post randomization (closest to study end as anchor for variables)
Supplemental Table 3 is the main Table 2 above by health system

Supplemental Table 4 is the main Table 2 above with OUD treatment related outcomes stratified by newly initiated treatmenta versus on-going treatmentb, and the OUD diagnosis outcome stratified by newly diagnosed OUDc versus prevalent OUDd.
 
a OUD treatment in the 2 years post randomization and no OUD treatment in the prior 365 days
 
b OUD treatment post-randomization that does not meet criteria for initiated above
 
c 1+ OUD diagnosis anywhere in the health system in the 2 years post randomization and no OUD diagnosis in the 2 years pre randomization.
 
d 1+ OUD diagnoses in both the 2 years pre randomization and 2-years post randomization

Supplementary Table 5. Sensitivity analyses focused on assumptions made in estimating patient-years of OUD medication treatment, clinic-level results in the 2 years post randomization			
	Patient years treatment /10,000 patients seen in clinic post-randomizationa		Mean difference (95% CI)b
	6 intervention clinics	6 usual care clinics	
Primary outcome			---
Limited to the time period in which the NCM started seeing patients d			
Limited to health systems that successfully implement the MA model e			
Covariate adjusted c			
Using a combination of medication orders and pharmacy dispensings			
Adding Methadone Maintenance Therapy data from 1-2 sites, per 10,000 patients seen in the 1-2 clinics post randomization			
Adding pharmacy dispensings and MMT data at the 1-2 sites with these sources of data			
Requiring 2+ orders/procedure codes to define treatment and omitting the last order			
Altering allowable gap to define continuous episodes of OUD treatment (main analysis allowable gap=7 days)			
2-day allowable gap			
5-day allowable gap			
10-day allowable gap			
Seen in the clinic pre-randomization			
OUD pre-randomization			
No OUD pre-randomization			
Patients new to the clinic post randomization			
Altering assignment of clinic to be the clinic with the most visits post randomization			
a Defined as having a medication order or procedure code for buprenorphine formulations that are indicated for OUD or having a medication order or procedure code for injectable naltrexone and 2+ visits with an OUD or OD diagnosis code (diagnosis codes can be during the 2-years pre or 2-years post randomization) b Mean difference in the primary outcome comparing clinics randomized to the PROUD intervention vs. clinics randomized to usual care, estimated from a random effects model adjusted for the primary outcome measure at baseline (two years prior to randomization) c Adjusted for {2 covariates determined from lasso regression} and baseline OUD treatment in random effects model			

Supplementary Table 6. Implementation of OUD medication treatment at the clinic-level in the 2 years post randomization stratified by patient characteristics, Primary Care Opioid Use Disorders Treatment (PROUD) trial			
	6 intervention clinics	6 usual care clinics	P value b
	Mean (SD) patient years of treatment across clinics per 10,000 patients in the subgroup		
Age at eligible visit closest to randomization a			
<26			
≥ 26			
Sex			
Female			
Male			
Race/Ethnicity			
Hispanic			
Non-Hispanic			
White			
Black			
Asian			
Other			

a Eligible primary care visits closest to and prior to randomization. If no eligible visits prior to randomization, post-randomization visit closest to randomization date was chosen.

b P values are presented for omnibus tests evaluating whether there is any difference in the intervention effect across subgroups, as well as for differences in subgroup-specific intervention effects, obtained from a linear mixed model with interaction terms between the intervention group and the subgroup

**Table 7.** Clinic level primary and secondary implementation outcomes of the Primary Care Opioid Use Disorders Treatment (PROUD) trial among patients receiving OUD treatment during the 2 years post randomization.

Randomization:			
Scaled implementation measure among treated patients	6 intervention clinics	6 usual care clinics	P value a
	Mean (SD) across clinics per 100 patients treated in the clinic post randomization		
Patient years of OUD treatment b			
Primary outcome (ITT analysis) c			
Limited to the time period after the NCM started seeing patients d			
Limited to health systems that successfully implement the MA model e			
Number of patients with:			
Newly initiated treatment a, f			
On-going treatment a,g			
80% of days covered by OUD treatment			
Newly initiated treatment a, f			
On-going treatment a,g			
≥ 6-months retention in OUD treatment h			
Newly initiated treatment a,f			
On-going treatment a,g			
Discontinuation of OUD treatment i			
Newly initiated treatment a,f			
On-going treatment a,g			
Buprenorphine average daily dose in mg			
Buprenorphine daily dose ≥16 mg j			
Naloxone prescription			

a Random effects model adjusted for the primary outcome measure at baseline (two years prior to randomization)

b Defined as having a medication order or procedure code for buprenorphine formulations that are indicated for OUD or having a medication order or procedure code for XR-NTX and 2+ visits with diagnosis code for OUD or opioid overdose (diagnosis codes can be during the 2-years pre or 2-years post randomization)

c Includes all clinics and all follow-up time post randomization

d Time period during which NCM seeing patients: X days for clinic A, X days for clinic B, X days for clinic C, X days for clinic D, X days for clinic E, and X days for clinic F

e Successful implementation defined as the nurse care manager seeing at least 30 patients. Analysis includes X of 6 health systems.

f OUD treatment in the 2 years post randomization and no OUD treatment in the prior 365 days

g OUD treatment in post-randomization, but not meeting criteria for initiated

h Restricted to subjects who entered the sample (i.e., had a PC visit) in the 1 day to 1.5 years post randomization (1 day to 12 months for the site randomizing 6-months late) to enable at least 6 months of follow-up

[figure not shown]
i defined as a gap in OUD treatment of 60 days

j 16 mg or more of buprenorphine/day at any time post randomization

[figure not shown]
Abbreviations: NCM – nurse care manager; ITT- intent to treat; OUD: opioid use disorder; SD – standard deviation; XR-NTX – extended release injectable naltrexone

